6.2.2. Rationale for Study Design

This present study is designed as a randomized, double-blind, Phase 3 study comparing TAS-102 plus best supportive care (BSC) to placebo plus BSC in patients with metastatic gastric cancer who have received at least 2 prior regimens for advanced disease and were refractory or unable to tolerate their last prior therapy.

A placebo-controlled design was considered appropriate as there are currently no standard therapies for patients with metastatic gastric cancer who have failed first- and second-line therapies.

Approximately 500 patients will be randomized 2:1 to TAS-102 plus BSC or placebo plus BSC. In order to ensure comparability of groups, patients will be stratified by geographic region (rest of world [ROW] vs Japan); Eastern Cooperative Oncology Group (ECOG) performance status (0 vs 1); and prior ramucirumab treatment (yes vs. no).

Overall survival was chosen as the primary endpoint because it is the gold standard endpoint for cancer indications in which there are no other therapy options with demonstrated survival benefit. Measurement of this endpoint is not questionable and patients with either measurable or non-measurable disease can be evaluated without the possibility of discrepancies in interpretations.

Standard safety assessments, including assessment of the type, incidence, severity (graded by National Cancer Institute [NCI] Common Terminology Criteria for Adverse Events [CTCAE], Version 4.03), timing, seriousness, and relatedness of AEs and laboratory assessments will be used.

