13.3.3. Safety Analyses

The safety evaluations will focus on AEs and laboratory assessments. All patients included in the AT Population will be evaluated by treatment arm in the safety analysis.

Adverse events will be coded according to the Medical Dictionary for Regulatory Activities (MedDRA) terminology and the severity of the toxicities will be graded according to the NCI CTCAE criteria, v4.03, where applicable. Concomitant medications will be coded according to the World Health Organization Drug Dictionary (WHODD). Hematological and chemistry laboratory parameters will be graded according to the NCI CTCAE v.4.03 criteria, where applicable.

All AEs will be summarized (incidence) and listed by the System Organ Class (SOC), preferred term (PT), toxicity/severity grade, and causal relationship to study medication. In addition, separate summaries of SAEs and Grade 3 and 4 AEs will be presented.

Absolute values and changes from baseline for hematology and serum chemistry parameters will be summarized by cycle. In addition, worst severity grade, and time to event will also be summarized.

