10.4. Analysis of the Primary Efficacy Endpoint

10.4.1. Primary Efficacy Analysis

OS in the ITT population will be compared between the 2 treatment groups (ITT population) using the stratified log-rank test (based on PROC LIFETEST, CCI  ). One- and 2-sided p-values will be presented. The study will be declared to have met its primary objective if the 1-sided p-value is be less than 0.0215 (please refer to [Section 12](#) for more details). The estimate of the hazard ratio (HR) and corresponding 95% CI will be provided using a Cox proportional hazards (CPH) model including treatment and the 3 stratifications factors in the model. Survival for each arm will be summarized using Kaplan Meier curves and further characterized in terms of the median and survival probability at 3, 6, 9 and 12 months, along with the corresponding 2-sided 95% CI for the estimates. The stratification factors will be populated as per the IXRS assignment.

Confidence intervals for median survival are based upon the methods of Brookmeyer and Crowley [16]. Confidence intervals for survivorship estimates are calculated using the log-log transformation [17] where the estimated variance of $\log(-\log(\hat{S}(t)))$ is:

$$\tau^2(t) = \sigma^2[\hat{S}(t)] / [\hat{S}(t)\log(\hat{S}(t))]^2 .$$

The 100 x (1- α)% confidence interval for $S(t)$ is given by:

$$[\hat{S}(t)]^{\exp(z_{\alpha/2}\tau(t))} \leq S(t) \leq [\hat{S}(t)]^{\exp(-z_{\alpha/2}\tau(t))}$$

CCI

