The number and percentage of patients with laboratory abnormalities of Grade 3 or Grade 4 that worsened from baseline by ≥ 1 grade or are missing at baseline will be summarized. For patients with more than 1 value recorded in a cycle/group of cycles, the abnormality with the highest grade will be selected for tabulation.

Time to event/worst grading will be assessed for selected clinical tests (hemoglobin, neutrophils, platelets) where CTCAE grading is available. The time to event/worst grading is defined as time from the date of the first dose of study medication to the date of the first occurrence of worst post-baseline CTCAE grade. If multiple events of the same worst grading occur, the earliest occurrence will be used. If no abnormal post-baseline values were recorded, the time to event/worst grading will be censored.

Presentation of the time to event/worst grading will be based on the Kaplan-Meier product-limit method is applied to estimate the mean, standard deviation, median, 25% percentile, and 75% percentile of the time to event/worst grading.

All observed (including unscheduled) laboratory parameters will be listed. The supportive listings for hematology, serum chemistry, and urinalysis will include the subject number, subject age and sex; laboratory test, lab test units, lab test result, and the lower and upper limits of normal (provided by the local laboratory where the test was performed); sample collection date, time of collection, and relative day; type of visit. The listing will be sorted by laboratory parameter, subject number, and by time points within laboratory parameter and subject number. Abnormal results will be flagged based on the categories mentioned above.

Specific rules how to handle clinical laboratory data can be found in the .

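### SAP 11.6 plans a Kaplan-Meier mean and standard deviation of time to worst haematology grade with no common restriction day, so the arm means are not comparable when a curve stays above zero

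*SAP*

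**What the plan says.** SAP 11.6 (Clinical Laboratory Data) sets up the summary in four steps.

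- Parameters: "Time to event/worst grading will be assessed for selected clinical tests (hemoglobin, neutrophils, platelets").
- Endpoint: "time from the date of the first dose of study medication to the date of the first occurrence of worst post-baseline CTCAE grade".
- Censoring: "If no abnormal post-baseline values were recorded, the time to event/worst grading will be censored". No censoring date appears in the readable text.
- Statistics: the "Kaplan-Meier product-limit method is applied to estimate the mean, standard deviation, median, 25% percentile, and 75% percentile of the time to event/worst grading". No upper limit of integration is given.

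Protocol 13.3.3 makes the comparison by arm: "All patients included in the AT Population will be evaluated by treatment arm in the safety analysis". Elsewhere the SAP handles censored times differently. OS (10.4.1) is summarised by the median and by survival at fixed months, and time to recovery from Grade 3 or 4 abnormalities (11.6.1) by the Kaplan-Meier median. Neither uses a mean.

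**The concern.** A mean event time is the whole area under the survival curve. If the longest follow-up time in an arm is censored, the curve stops above zero and the rest of that area is unobserved. Any figure printed as the mean is then the area up to some limit. Unless the plan fixes that limit, it is set by the arm's own last event or own last observation. It then depends on how few events there were, or on who was followed longest, rather than on toxicity.

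The standard deviation has the same difficulty. It needs the same unobserved tail, and what the method supplies is the sampling variance of the truncated area.

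A reader who compares the two means could therefore be comparing areas cut at different days. In an unfavourable case the arm with less marrow toxicity would show the shorter mean time to it.

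**Working it through.** The documents state no figure for this summary, so there is none to reproduce.

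**Formulas.** For limit L, mean(L) = ∫₀ᴸ S(t) dt. Its variance is Σⱼ [∫ from tⱼ to L of S(u) du]² · dⱼ / [nⱼ(nⱼ − dⱼ)], summed over event times tⱼ.

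**Hand example.** "Approximately 500 patients will be randomized 2:1 to TAS-102 plus BSC or placebo plus BSC" gives 500 × 2/3 ≈ 333 and 500/3 ≈ 167. Assume one placebo event at the Day 15 sample and all 167 placebo patients still observed then. S = 1 to day 15, then 166/167 = 0.994.

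- Closed at the last event: mean = 15 days, standard error = 0.
- Closed at day 84 (three 28-day cycles): mean = 15 + 69 × 0.994 = 83.6 days; standard error = √[68.6² / (167 × 166)] = 0.41 days.

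The same data give 15 or 83.6 days according to the limit. Neither 0 nor 0.41 describes the spread of event times.

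**Simulations.** From the documents: arm sizes and the laboratory schedule (Cycle 1 Day 15, then before each cycle). Assumed: event rates, follow-up and the truncation rule. Wrong order means that TAS-102, given the higher risk, has the longer mean.

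*Set A.* Median laboratory follow-up beyond Day 15 of 55 v 35 days; constant risk per sample; 400 trials per scenario. Ranges cover two separate runs or several scenarios.

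| Risk per sample, TAS-102 v placebo | Closed at last event | Closed at last observation |
|---|---|---|
| 10% v 1% | 173–175 v 90–97 days; wrong in 88–90% | 199 v 266–270 days; wrong in 16% |
| 5% v 1% | wrong in 94–95% | wrong in 71% |
| 20–30% v 1–2% | wrong in 14–63% | wrong in 0% |

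*Set B.* Exponential treatment duration, median 60 days on TAS-102 and 45 on placebo; censoring at the last sample; 200 trials per scenario. The first three rows fix the share of patients ever abnormal, and the last two fix the risk per visit.

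| TAS-102 v placebo | Closed at last event | Closed at last observation | Common day 84 |
|---|---|---|---|
| 40% v 10% | 194 v 147; wrong in 76% | 258 v 340; 14% | 68 v 80; 0% |
| 40% v 20% | 196 v 161; 76% | 263 v 283; 41% | 68 v 75; 0% |
| 65% v 40% | 128 v 138; 43% | 142 v 192; 9% | 58 v 67; 0% |
| 0.15 v 0.01 per visit | 138 v 136; 55% | 147 v 361; 0% | 65 v 83; 0% |
| 0.35 v 0.02 per visit | 58 v 175; 2% | 59 v 326; 0% | 45 v 81; 0% |

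With a placebo median of 60 days, reversal is less frequent: at 40% v 10% it falls from 76% to 55% at the last event and from 14% to 1% at the last observation. Over all Set B scenarios with a placebo share of 0.40 or less, a common day 84 ranks the arms correctly in at least 99% of trials. At 65% v 60% there is little true difference to rank, so those runs are uninformative.

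*Set C.* Event coded as the SAP defines it, the first occurrence of the worst grade. With about 30% v 3% having the event, the order is wrong in 88% (last event) and 12% (last observation). With 65% v 8% it is wrong in 15% and 0%, and with 82% v 24% in 0%. With a common day 84 it is 0% throughout.

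**The case against.** Five points can be made for the plan.

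1. *Heavy placebo censoring is not documented.* A reader might infer that most placebo patients will be censored for neutrophils and platelets. The documents give no placebo rate. Any abnormal value counts, including a mild one already present at baseline, and the entry limits (ANC at least 1,500/mm³, platelets at least 100,000/mm³; Protocol 8.3.1) are absolute rather than tied to the local lower limit of normal. Heavy censoring is plausible, no more.
2. *The last-event cut-off is not in the SAP.* A reader might take "based on PROC LIFETEST" as fixing a software convention. That phrase belongs to the OS log-rank test in 10.4.1, and closing at the last observation often restores the right order.
3. *The rule may be redacted.* The subsection ends with "Specific rules how to handle clinical laboratory data can be found in the" and then a gap. A restriction day or censoring date could be there. A common day would repair the mean but would not turn a standard error into a standard deviation.
4. *Worst grade looks ahead.* A patient treated for longer can reach the worst grade later, so a longer mean on TAS-102 is not automatically an error. This limits how Sets A and B can be read. Set C uses the SAP definition and still shows the reversal, which a common limit removes. The look-ahead itself would remain in any fixed-day percentage.
5. *Little depends on the table.* It is descriptive, with no test attached. The median and quartiles are in the same sentence, and the SAP also plans Grade 3/4 counts and percentages, shift tables and patient-time rates with Poisson intervals.

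Points 1, 2 and 5 stand and limit the size of the concern. None of the five makes an unrestricted mean, or a standard deviation, estimable from a curve that stays above zero.

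**Conclusion.** The point holds as a minor flaw in a stated method. Whenever an arm's curve does not reach zero, the planned mean is an area to an arm-specific limit, the planned standard deviation is not estimable, and the arm means should not be compared. This follows from the estimator and needs no assumed rate.

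Reversal of the arms is a further possibility that does depend on assumptions. It is frequent at low event rates with closure at the last event, and usually less frequent with closure at the last observation (although 71% in one low-rate case). It is rare or absent at high TAS-102 rates. The one relevant drug figure in the documents, 69.0% Grade 3 or 4 neutropenia among 29 Phase 2 patients (Protocol 6.1.2.2), suggests the higher-rate setting for neutrophils. Platelets could lie lower, but no rate is given. The documents therefore do not support saying that the arms will rank wrongly. The trial's conclusions are not affected.

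**What to change.** In the SAP 11.6 sentence, delete the mean and standard deviation. If a mean is wanted, replace them with a restricted mean and its standard error to one day fixed before unblinding and used in both arms. Day 84 served here as an illustration; the choice is the sponsor's. If the redacted laboratory rules already set such a day, cite it in the sentence and still drop the standard deviation.

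Keep the median and quartiles, shown only where reached, and state the censoring date. Optionally add the percentage with the event and its 95% CI at common fixed days, such as Day 15 and the ends of Cycles 1 to 3.

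The cost is one sentence and a small table-shell change, with no new data. It brings this summary into line with how the SAP already reports OS and time to recovery.

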11.6.1. Hematology

The following test will be summarized and tabulated, all other hematology tests will be listed only:

Red blood cells count (RBC)	White Blood Cells (WBC)	
Hemoglobin	Neutrophils (absolute value)	Neutrophils (%)
Hematocrit	Lymphocytes (absolute value)	Lymphocytes (%)
Platelets	Monocytes (absolute value)	Monocytes (%)
	Eosinophils (absolute value)	Eosinophils (%)
	Basophils (absolute value)	Basophils (%)

The “most extreme value” recorded, and the corresponding number of days to the most extreme value recorded, will be summarized descriptively for Grade 3 or 4 abnormalities. This will be limited to the following selected “parameters of interest”: hemoglobin, neutrophils and platelets for the “most extreme” is defined as the value of smallest magnitude. Additional parameters may be added to this analysis as appropriate.

The median number of days to ‘recovery’ (Section 8.10) in patients with Grade 3 or 4 abnormalities that worsened from baseline will be obtained from Kaplan-Meier estimates.

Shift tables showing changes in the NCI CTCAE grade from baseline to the worst grade recorded post-baseline are tabulated. Parameters with NCI CTCAE criteria defined bi-directionally have low value abnormalities represented by a negative sign so that they may be differentiated from high value abnormalities. If the NCI CTCAE criteria are uni-directional the negative sign is not used even if the criteria are defined to flag low value abnormalities.

The rate per 100 patient years (see Section 8.9 for the appropriate details) of Grade 3 or 4 abnormalities in hemoglobin (low), neutrophils, and platelets, along with the corresponding 95% Poisson CIs, will be summarized.

11.6.2. Serum Chemistry

The following test will be summarized and tabulated, all other serum chemistry tests will be listed only:

ALT (SGPT)	Creatinine	Chloride
AST (SGOT)	Blood urea nitrogen (BUN)	Calcium
Alkaline phosphatase	Sodium	Albumin
Bilirubin	Potassium	Glucose

In case of elevation in total bilirubin, fractionation (direct/indirect) should be performed and listed.

11.6.3. Urinalysis

Urinalysis will include tests for protein, glucose, urobilinogen, RBC, and WBC. If a new abnormality is identified during the Study, quantitative urinalysis should be performed.

CCI

11.7. Vital Signs

Vital signs (VS) will include: systolic/diastolic blood pressure, body temperature, heart rate, respiratory rate and weight. To integrate VS evaluations with different collection times, they will be summarized by analysis visit cycles as specified at [Section 4.1.2](#).

The presentation of VS results will focus on the change from baseline to post-dose on treatment evaluations. All patients who had a baseline and at least one post-dose on-treatment VS assessment will be included in the presentation of the VS data. If multiple results are reported at an analysis time window (refer to [Section 8.7](#) and [CCI \[REDACTED\]](#)), then the logic described in [Section 8.8](#) and specific data handling rules presented in [CCI \[REDACTED\]](#) will be applied. Tables of descriptive statistics for vital signs will present both actual values and change from baseline values. Summary statistics will include number of subjects, mean, standard deviation, median, minimum and maximum.

11.8. ECG

ECG data were not collected.

11.9. Physical Examination

According to the recent updates in CDISC “Guide for implementation” the results of physical examination (abnormalities only) are collected as part of adverse events or medical history (based on the appropriate dates and time). Therefore, results of the physical examination will be not summarized as separate tables.

12. INTERIM ANALYSES

One interim analysis for efficacy and futility is planned for the study after approximately 1/2 of the total target events are observed (192 deaths). The Lan-DeMets alpha-spending approach will be used with O'Brien-Fleming stopping boundaries to guide the efficacy evaluation at the interim and final OS analysis. This approach will account for multiple testing and preserve the overall 1-sided study significance level of 0.025. A fixed HR boundary will be used to assess futility (non-binding). Stop due to futility will be recommended if observed HR will be ≥ 0.95 when conditional power is less than 2%. Stopping the study for efficacy will be recommended if calculated 1-sided p-value is less than 0.0015. The corresponding HR for such significant results is less than approximately 0.63, associated with a median OS improvement from 5 to 7.9 months. The exact boundaries will be derived based on the actual number of events used for the interim analysis.

For the final analysis of the primary efficacy endpoint the result will be considered as significant if 1-sided p-value will be less than 0.0245. The corresponding HR for such significant result is less than approximately 0.808 associated with a median OS improvement from 5 to 8 months). Additional details are provided in the DMC charter.

The interim analysis was performed based on 220 events (deaths) reported as of August 31, 2017. The associated efficacy boundary suggested to the DMC was 1-sided p-value of 0.0031. (C)

Considering the alpha-spending that took place for the interim analysis the associated efficacy boundary for the final analysis (assuming 384 events as planned) is 1-sided p-value of 0.0215.

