14. CHANGES IN/ CLARIFICATIONS TO THE CONDUCT OF THE STUDY OR PLANNED ANALYSIS

Since the version 1.05 of the SAP (06JULUL2016) was approved, the following clarifications/changes were made in the text of the SAP:

- Reference date for age calculation was changed from randomization date to the date of informed consent (Section 8.1).
- Definitions for Cycle windows (Section 8.7) and handling of Multiple Assessments (Section 8.8) were further detailed and documented in SAP CCI (‘‘Data Handling Guidance’’).
- Time Adjusted Incidence Rate calculations were revised from 1 year to 100 years (Section 8.9).
- Creatinine Clearance levels for the severe renal function impairment group were added to the definition (Section 8.11).
- Imputation rules for partial birth dates, missing end of exposure dates, and start of antitumor therapy dates were added (Section 8.13)
- Definitions of CSR Reportable Protocol Deviations were added to the existing Major Protocol Deviations (Section 9.2).
- Part of the demographic and baseline characteristics summaries was relocated under cancer medical history (Section 9.3 and Section 9.5.1).
- Details of how the prior cancer medical history are summarized were updated (Section 9.5.1).
- Details of how the prior anti-cancer therapies are summarized were updated (Section 9.6.1).
- Medical history will be summarized for AT, instead of the ITT population (Section 9.5).

CCI

- SAS code for the primary efficacy analysis was documented CCI

CCI

CCI

- List of TEAE summaries was updated (Section 11.2.1).
- The efficacy boundary (p-value) for the final analysis was derived, based on the actual event count used for the interim analysis (Section 12).
- A Data Handling Guidance appendix was added CCI that further details data handling rules for safety endpoints.
- PFS Censoring rules were updated CCI
- Standard lab ranges were updated to include the normal range for Indirect Bilirubin CCI.
- Date for the clinical cut-off was established and rules for submission database were added CCI

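### The final OS boundary of 1-sided 0.0215 does not follow from the SAP's stated spending method and event counts, which give 0.0240; the discrepancy is conservative

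*SAP*

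**What the plan says.** SAP Section 12 specifies one interim and one final analysis of OS, with Lan-DeMets alpha spending and O'Brien-Fleming boundaries, intended to "preserve the overall 1-sided study significance level of 0.025". The futility rule is non-binding. For the planned interim at 192 deaths the section gives a 1-sided efficacy boundary of 0.0015. For the final analysis, the "result will be considered as significant if 1-sided p-value will be less than 0.0245", with a corresponding HR "less than approximately 0.808 associated with a median OS improvement from 5 to 8 months".

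The section then reports what happened: "The interim analysis was performed based on 220 events (deaths) reported as of August 31, 2017". The threshold used at that look is given next: "The associated efficacy boundary suggested to the DMC was 1-sided p-value of 0.0031". After a blacked-out fragment it concludes that "the associated efficacy boundary for the final analysis (assuming 384 events as planned) is 1-sided p-value of 0.0215".

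Section 10.4.1 adopts that figure: the primary objective is met "if the 1-sided p-value is be less than 0.0215". Section 14 lists the change and its basis: "The efficacy boundary (p-value) for the final analysis was derived, based on the actual event count used for the interim analysis".

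**The concern.** The SAP presents 0.0215 as a derived number and shows the inputs: the spending method, overall alpha of 0.025, 220 interim deaths, an interim boundary of 0.0031 and 384 final deaths. With so little alpha spent at the interim, an O'Brien-Fleming-type design should leave a final boundary close to 0.025. A drop from 0.0245 to 0.0215 is too large for a move from 192 to 220 interim deaths.

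This number decides the primary endpoint, and SAP Section 10.3 makes PFS testing conditional on OS significance. If it is wrong in this direction, validity is not at risk, but a result that the stated design accepts could be reported as a failure.

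Two smaller points sit in the same section. The planning value 0.0245 is still worded as the criterion for the final analysis, with nothing to say it has been replaced. The median gain attached to HR 0.808 also does not match that HR.

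**Working it through.** **Inputs.** From SAP Section 12: overall 1-sided alpha 0.025, planned interim 192 deaths, actual interim 220 deaths, final 384 deaths, non-binding futility (so it does not enter the efficacy boundary). From SAP Section 4.3.1: 2:1 allocation, design HR 0.70.

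**Method.** The O'Brien-Fleming-type spending function is a(t) = 2 × [1 − Φ(2.2414/√t)], where 2.2414 is the normal quantile at 1 − 0.025/2. The interim critical value c1 satisfies P(Z1 ≥ c1) = a(t). The final critical value c2 solves a(t) + P(Z1 < c1, Z2 ≥ c2) = 0.025, with corr(Z1, Z2) = √t.

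**Planning values first.** At t = 192/384 = 0.5, 2.2414/√0.5 = 3.170 and a = 0.00153. Solving for the final look gives 0.0245.

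**Actual interim.** At t = 220/384 = 0.5729, √t = 0.7569 and 2.2414/0.7569 = 2.961, so a = 0.00306 and c1 = 2.741. Solving for the final look gives c2 = 1.977, a 1-sided p of 0.0240.

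| Boundary (1-sided p) | SAP | Recomputed |
|---|---|---|
| Interim at 192 deaths | 0.0015 | 0.00153 |
| Final, as planned | 0.0245 | 0.0245 |
| Interim at 220 deaths | 0.0031 | 0.00306 |
| Final after interim at 220 deaths | **0.0215** | **0.0240** |

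Three of the four figures match, so the choice of spending function is not in doubt.

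**Can anything visible produce 0.0215?**

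- Rounding: interim spends from 0.00305 to 0.00315 all give 0.0240.
- Simple subtraction: 0.025 − 0.0031 = 0.0219. This is a floor, because P(Z1 < c1, Z2 ≥ c2) cannot exceed P(Z2 ≥ c2). A design that spends 0.0031 and uses the full 0.025 cannot go lower.
- A different final count: with 0.0031 spent, 370 deaths gives 0.0241, 400 gives 0.0239 and 420 gives 0.0238.
- Other constructions: classic O'Brien-Fleming gives 0.0234, halved two-sided 0.05 spending 0.0231, Pocock-type spending 0.0131, and binding futility at HR 0.95 gives 0.0245.
- Solving backwards: the stated function gives 0.0215 only if the interim falls at about 305 of 384 deaths (t = 0.795, spend 0.0120). With the interim at 220 deaths, about 0.0075 would have to be spent already, and 0.0075/0.0031 = 2.4 times the stated boundary.

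**Overall alpha with 0.0031 at the interim:**

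| Final boundary | Alpha added at final look | Overall 1-sided alpha |
|---|---|---|
| 0.0215 | 0.0195 | 0.0226 |
| 0.0240 | 0.0219 | 0.0250 |
| 0.0245 | 0.0224 | 0.0255 |

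A simulation of 20 million pairs of test statistics gave the same overall values. Unused alpha under 0.0215 is 0.0250 − 0.0226 = 0.0024.

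**Effect on the decision.** With 2:1 allocation, SE(log HR) = 1/√(384 × 2/9) = 0.1083. The critical HR is exp(−2.024 × 0.1083) = 0.803 at 0.0215 and exp(−1.977 × 0.1083) = 0.807 at 0.0240. Group-sequential power at HR 0.70 is 89.9% and 90.7% respectively. The chance that the choice of boundary changes the conclusion is 0.8% at HR 0.70, 1.4% at 0.75 and 1.8% at 0.80.

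**Median gain.** Section 12 pairs its interim HR of about 0.63 with 7.9 months, which is 5/0.63. By the same rule, HR 0.808 gives 5/0.808 = 6.2 months. The printed 8 is close to the interim figure of 7.9.

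**The case against.** The strongest objection is that the link between 0.0031 and 0.0215 cannot be seen. A blacked-out fragment stands between the two, and Section 12 refers to a DMC charter that is not available. The visible text calls 0.0031 the boundary suggested to the DMC; it does not say that this is all the alpha that was spent. A total interim spend near 0.0075 would give 0.0215. This stands as a limit on the finding: what is shown is that the stated method and figures do not yield 0.0215, not that no reason exists. No visible text mentions any further spending.

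It is also fair to say that the harm is small. The rule is strict, Sections 10.4.1 and 12 both state it, power stays at about the planned 90%, and 0.025 is still respected as an upper bound. Loosening a primary threshold after an interim efficacy look invites questions out of proportion to a gain of under one point of power. That stands too, and it is why keeping 0.0215 is an acceptable outcome.

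On 0.0245, Section 12 says beforehand that the exact boundaries will be re-derived, and Section 10.4.1 names only 0.0215. A careful reader can tell which value governs, so this is a point of clarity with little weight. The median slip affects no decision rule.

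**Conclusion.** The concern holds. From the method and counts that the SAP states, the final 1-sided boundary is 0.0240, and 0.0215 lies below even the 0.0219 that plain subtraction leaves. The departure is conservative: overall alpha 0.0226 instead of 0.0250, critical HR 0.803 instead of 0.807, and 0.8 points of power lost at HR 0.70. Type I error would exceed 0.025 (reaching 0.0255) only if the planning value 0.0245 were applied after the interim at 220 deaths.

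The conclusion assumes that 0.0031 is the whole interim spend, that futility is non-binding as stated, and that the final analysis is at or near 384 deaths. The HR and power figures also assume proportional hazards and the usual variance approximation for 2:1 allocation. It should be fixed because it is the pass/fail threshold of the trial and cannot be traced to its stated derivation, not because the test is invalid.

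**What to change.** Before unblinding, check the calculation behind 0.0215 against the stated spending function.

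- If nothing beyond that function was intended, change the boundary to 0.0240 in SAP Sections 10.4.1 and 12, re-derive it if the final count is not 384, and document the calculation. Because this relaxes the threshold after an efficacy look, log it in Section 14 as a correction based on event counts alone and made without knowledge of interim results.
- If 0.0215 is deliberate, keep it. State that it is stricter than the spending function requires and give the overall 1-sided alpha as about 0.0226. This takes one sentence and raises no question about a post-interim change.

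In either case, label 0.0245 as the superseded planning value for an interim at 192 deaths, and change the median gain paired with HR 0.808 to about 5 to 6.2 months.

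The cost is SAP wording only: no new data, no change to conduct and no effect on sample size.
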